#### 5.1.3 Analysis Population

All subjects who have been randomized and treated at the time of data snapshot for this analysis. All available data from these subjects will be included in the analysis.

## 5.1.4 Procedures

a. Cut-off dates for eCRFs, data cleaning, and analysis will be established based on an estimated target date of the 25% (~100 subjects) or 75% (~300 subjects) treated subject completing 2 weeks of randomized treatment.

- All data received by the cutoff date will be entered, validated, queries generated and resolved or pending queries documented.
- The data snapshot will be taken. This database will not contain the treatment assignments (i.e., will be blinded).
- d. The data snapshot will be saved in a drive to which only the independent statistician responsible for the safety analysis has access.
- e. The randomization code to un-blind the data will be delivered to the independent statistician by the IWRS master for the study.
- f. The independent statistician will merge the randomization code with the data and will generate planned data and information for the DSMC, as described below.

### 5.1.5 Data and Information Provided to DSMC

The DSMC will receive the following data: disposition, demographics, AEs, SAEs, and death. No inferential statistics will be conducted for this safety analysis.

#### 5.1.6 Stopping Rule

There is no intention of stopping the study as a result of this safety analysis. However, DSMC may recommend stopping the trial for safety reasons at any time.

### 5.1.7 Information Provided to Sponsor by DSMC

Following each meeting, formal minutes, including any recommendations for continuation or modification of the trial, will be prepared according to the procedure outlined in the DSMC Charter. These minutes will not contain any information or comments that might possibly unblind the trial.

#### 5.1.8 Type I Error Rate Adjustment

No type I error adjustment will be made due to this safety analysis.

As there are no planned inferential statistics, the type I error rate for the final analysis will not be inflated because of this interim analysis.

## 5.2 Efficacy Interim Analysis

An efficacy Interim Analysis (IA) will be conducted when approximately 50% (~195 subjects) have been randomized and completed 4 weeks of randomized treatment or are withdrawn from the study, whichever occurs first.

#### 5.2.1 Objectives of this IA

The main objective of the IA is sample size re-assessment.

#### 5.2.2 Analysis Population

The IA population will be approximately 50% (~195 subjects) who have been randomized and completed 4 weeks of randomized treatment or are withdrawn from the study, whichever occurs first.

### 5.2.3 Procedures for the IA

The procedures for this IA will be based on a standard operating procedure (SOP) that has a wellestablished firewall to protect the integrity of the trial. The IA will be performed by an independent un-blinded statistician, who is not otherwise associated with the conduct of this trial. The procedures include the following:

- a. Cut-off dates for collection of eCRFs, data cleaning, database lock and analysis will be established based on an estimated target date of 50% of subjects have completed 4 weeks of randomized treatment or are withdrawn from the study.
- b. All data received by the cutoff date will be entered, validated, queries generated and resolved or pending queries documented.
- c. The database will be locked for the IA. This database will not contain the treatment assignments (i.e., will be blinded).
- d. The locked database will be saved in a drive to which only the independent statistician responsible for the IA has access.
- e. The randomization code to un-blind the data will be delivered to the independent statistician by the IWRS master for the study.
- f. The independent statistician will merge the randomization code with the validated data and will generate planned data and information for the DSMC.

#### 5.2.4 Metrics to be Calculated for the IA

Using IA unblinded data, the independent statistician will prepare disposition, summaries along with a conditional power (CP) using the primary endpoint data. The CP will be calculated for using the difference in mortality between the leronlimab and the placebo group.

The sample size re-assessment will be based on CP. The CP will be calculated based on:

- 1. The Day 28 mortality rate in the leronlimab group (PA) and the observed number of subjects in the group
- 2. The Day 28 mortality rate in the placebo treatment group (Pp) and the observed number of

subjects in the group

- 3. The difference in mortality rate between  $P_A$  group and  $P_P$  group  $(P_A P_P)$
- 4. The CP of the study at the time of the IA (The method for this calculation is provided in Section 5.5.

#### 5.2.5 Conditional Power

The CP will be calculated according to the below formula (Chen, 2004) using the response rate between PA group and Pp group:

$$CP(f_l, Z) = \Phi \{ -Z_{\alpha} / \sqrt{(1-f_1)} + Z / \sqrt{f_1(1-f_1)} \}$$

Where:

- $CP(f_1, Z)$  is the CP at the IA
- $\Phi$ {.} is the cumulative distribution function of a Standard Normal distribution ( $\mu$ =0,  $\sigma$ =1)
- $f_1$  is the fraction of patients enrolled and used in the IA before decision of increasing the sample size, which is 50% for this protocol  $(f_1 = (n_A + n_p) / N_A + N_p)$ , where  $n_A$  and  $n_p$  are the number of subjects used for the IA in the leronlimab and the placebo groups, respectively, and  $N_A + N_p$  is the original sample size  $(N_0)$  for the two groups)
- $Z_{\alpha}$  is the upper (1- $\alpha$ ) percentile for standard normal distribution
- Z is the test statistics at the IA:

$$Z = \frac{\hat{\delta}}{\operatorname{se}(\hat{\delta})}$$

Where:

[figure not shown]
•  $\hat{\delta}$  = the maximum likelihood estimate of the proportion difference calculating from logistic model at IA

The resulting CP will be used to determine whether the sample size needs to be increased or remain unchanged.

## 5.2.6 Rules and Method for Increasing Sample Size

Rule: The sample size for the study is planned to be adjusted only if the CP at the IA is less than 90% and greater than 35% (i.e., out of the promising zone). The adjustment would be an increase in the sample size in order to bring the CP to at least 90% up to a maximum increase of 1170 subjects (780 for leronlimab group and 390 for the placebo group), using the observed differences at the time of

the IA. The sample size is to be maintained as the original sample size, if the CP is larger than or equal to 90% or less than 34%. The promising zone is depicted in the below figure.

Method: This sample size recalculation will be made by adjusting the  $f_2$  in the CP equation below:

$$CP(f_2, Z) = \Phi \{ -Z_{\alpha} / \sqrt{(1-f_2)} + Z / \sqrt{f_2 (1-f_2)} \}$$

Where:

- CP( $f_2$ , Z) is the CP at the IA to be increased to 80% by adjusting  $f_2$
- $f_2$  is the fraction of subjects enrolled and used in the IA before decision of increasing the sample size relative to the new sample in the adjusted trial. It is defined as:

$$f_2 = (n_b + n_p) / (N_0 + n_{added})$$

•  $\Phi$ {.},  $Z_{\alpha}$ , Z,  $n_b$ ,  $n_p$  and  $N_0$  are the same as those defined above

The number of subjects to be added to the trial is then calculated from the  $f_2$  that yields the CP of 90% as follows:

$$n_{added} = (n_b + n_p - N_0 * f_2) / f_2$$

### 5.2.7 Type I Error Rate Adjustment Due to the IA

There will be no statistical penalty on the Type I error rate due to the IA as the sample size will be increased only if the conditional power calculated at the IA falls into the promising zone.

#### 5.2.8 Data Provided to DSMC

The DSMC will receive a statistical report. The report will include disposition, demographics, mortality data and safety summaries. Besides the mortality data, the report will also include descriptive summary of key outcome indicators such as, change in clinical status based on a 7 point ordinal scale and total duration of hospitalization, ICU, and mechanical ventilation use.

#### 5.2.9 Stopping Rule

The trial will not be stopped for efficacy reasons.

## 5.2.10 Information Provided to Sponsor by DSMC

The DSMC will only make recommendations to sponsor on the sample size adjustment in a blinded fashion.

#### 6. PRIMARY HYPOTHESIS TO BE TESTED

The primary hypothesis to be tested for this study is:

 $H_0$ :  $P_{leronlimab} = P_{Placebo}$  (i.e. there is no difference in the Day 28 mortality rate between the two treatment groups)

 $H_1$ : Pleronlimab  $\neq$  PPlacebo (i.e. there is difference in the Day 28 mortality rate between the two treatment groups)

#### 7. ANALYSIS POPULATIONS

#### 7.1 Modified Intent-to-Treat Population

The **Modified Intent-to-Treat (mITT) population** is defined as the set of subjects who randomized and have received at least one dose of leronlimab (PRO 140) or placebo. This population will be used as the primary analysis population for analysis of the primary and secondary efficacy endpoints.

#### 7.2 Intent-to-Treat Population

The Intent-to-Treat (ITT) population is defined as all randomized subjects. This population will be used as the sensitivity analysis for analysis of the primary and secondary efficacy endpoints.

### 7.3 PP Population

The **Per Protocol (PP) population** is defined as the set of subjects who meet the ITT Population requirements and are not associated with any major protocol violations per ICH definition including:

- · Informed consent not properly attained
- Did not meet inclusion/ exclusion criteria but entered into study

Note: Subjects who have confirmed COVID-19 diagnosis but results not available within 5 days of screening will not be considered major protocol deviation/violation.

- Developed withdrawal criteria during the study, but not withdrawn
- Study drug dosing deviation

Note: Subjects who do not receive two doses of study treatment (except in case of mortality within 7 days of treatment initiation) will be considered major protocol deviation/violation and will be excluded from the PP population.

Received excluded concomitant medication

This population will be identified programmatically before the database lock. This population will be used as the supportive analysis population for analysis of the primary and secondary efficacy endpoints.

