Screening assessments will commence at Visit 1 (V1) after obtaining signed informed consent, and will include review of medical and medication history, eligibility evaluation, subject demographics, physical examination, vital signs, clinical status – ordinal scale assessment, PaO2/FiO2 measurement, pulse oxygen saturation (SpO2), positive end-expiratory pressure (PEEP), (for intubated subjects), National Early Warning Score 2 (NEWS2) assessment, electrocardiogram (ECG), nasopharyngeal swab sample collection, chest radiograph or CT (if clinically indicated), assessment for the requirement of: mechanical ventilation, non-invasive ventilation, supplemental oxygen, vasopressors use, renal replacement therapy, ICU admission and hospital stay, and laboratory sample collection for routine serum biochemical, hematologic, coagulation, urinalysis, and serum/urine pregnancy (if applicable). These assessments must be conducted within 7 days of the First Treatment Visit (V2).

All subjects who fail to meet eligibility criteria are considered screen failures, and are exited from the study without further evaluation.

Treatment Period (2 weeks \pm allowed windows):

The schedule of visits during Treatment Period is as follows:

- Visit 2 (V2) [first treatment]: Within 1 week of the Screening Visit
- Visit 3 (V3): 3 (±1) day after V2
- Visit 4 (V4) [second treatment]: 7 (±1) days after V2
- Visit 5 (V5) / End of Treatment (EOT) Visit: 7 (±1) days after V4.

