5.3. REMOVAL OF SUBJECTS FROM STUDY TREATMENT AND/OR STUDY AS A WHOLE

Subjects can be taken off the study treatment and/or study as a whole at any time at their own request, or they may be withdrawn at the discretion of the investigator for safety, behavioral or administrative reasons. In the case that a subject is removed from the study due to safety reasons, the FDA and other global regulatory authority will be notified. The reason(s) for discontinuation must be clearly documented on the appropriate eCRF and may include:

- Subject voluntarily withdraws from treatment (follow-up permitted)
- Subject withdraws consent (no follow-up permitted)
- Subject is unable to comply with protocol requirements

CONFIDENTIAL Page 61 of 108

- Subject experiences unacceptable toxicity
- Treating physician determines that continuation on the study would not be in the subject's best interest
- Subject becomes pregnant
- Subject becomes lost to follow-up (LTF)
- Subject will be withdrawn from the study if 2 consecutive injections of study drug are missed
- Subject manifesting Grade 4 or Grade 3 toxicity attributable to the Leronlimab (PRO 140)

If a subject fails to return for the scheduled study visit or is discontinued from the study, an attempt will be made to determine the reason(s). If the subject is unreachable by telephone, a registered letter will be sent to the subject requesting that he/she contact the clinic.

All patients with an ongoing SAE or AE attributable (definitely, probably, or possibly related) to the study treatment at the Post-Study (Follow-up) Visit (scheduled or premature) must be followed until the event is resolved (with or without sequelae) or deemed stable.

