6.1.5. Leronlimab (PRO 140) - Toxicity Management

Refer to Table 6-3 and Table 6-4

Table 6-4below. Recovery to acceptable levels must occur to allow leronlimab (PRO 140) continuation.

Table 6-3: Leronlimab (PRO 140) - Management for Injection Site Reactions

CTCAE Grade	Treatment Management
Grade 1	No dose adjustment is required.
Grade 2	First Occurrence: No dose adjustment is required. Second Occurrence of the same event: Closely follow-up for resolution of the AE to Grade ≤ 1
Grade 3	Withhold treatment until symptoms resolve to: • Grade 1 or less
Grade 4	Study treatment will be permanently discontinued

CONFIDENTIAL Page 66 of 108

Table 6-4: Leronlimab (PRO 140) - Management for all Other Potential Toxicities

CTCAE Grade (attributable to leronlimab)	Treatment Management
Grade 1	No dose adjustment is required.
Grade 2	Withhold treatment until symptoms resolve to: • Grade 1 or less or baseline;
Grade 3	Study treatment will be permanently discontinued
Grade 4	Study treatment will be permanently discontinued

(Attributable to Leronlimab)

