8.10.5. Supportive Analysis

To assess the consistency of the Primary Analysis results, supportive analysis will be conducted using the Intent to Treat (ITT) and Per Protocol (PP) populations. Statistical methodology for the supportive analyses will be the same as that of the primary analysis, with the exception of the analysis population used.

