# 9.2 Analysis of Efficacy Data

The primary analysis will be conducted on the mITT population. The PP population will be used as a supportive analysis if there is at least 5% difference between the numbers of subjects in the two populations. All statistical tests for efficacy will be two-sided tests, with  $\alpha$ =0.05

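### The SAP's per-protocol rule excludes subjects who missed dose 2 as the protocol directs, or who died on Day 8 inside the dosing window, and SAP 9.2's 5% condition on the analysis conflicts with SAP 7.3 and the protocol

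*SAP*

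**What the plan says.** SAP 7.3 lists the major violations that remove a subject from PP. The note under study drug dosing deviations covers "Subjects who do not receive two doses of study treatment (except in case of mortality within 7 days of treatment initiation"), and says that these subjects "will be considered major protocol deviation/violation and will be excluded from the PP population". Membership is to be determined by program before database lock.

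Protocol 6.1.5 sets the toxicity rules. For a Grade 4 injection-site reaction (Table 6-3), and for any other attributable Grade 3 or 4 toxicity (Table 6-4), the instruction is "Study treatment will be permanently discontinued". For a Grade 3 injection-site reaction (Table 6-3), and for any other attributable Grade 2 toxicity (Table 6-4), it is "Withhold treatment until symptoms resolve to" a lower grade.

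Protocol 5.3 includes, among the reasons for discontinuation, "Subject manifesting Grade 4 or Grade 3 toxicity attributable to the Leronlimab (PRO 140").

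The timing of dose 2 in the protocol synopsis, repeated in Protocol section 4 and SAP 2.2, is "Visit 4 (V4) [second treatment]: 7 (±1) days after V2".

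SAP 9.2 uses PP as a supportive analysis "if there is at least 5% difference between the numbers of subjects in the two populations". Protocol 8.10.5 says that "supportive analysis will be conducted using the Intent to Treat (ITT) and Per Protocol (PP) populations", without a condition. SAP 7.3 and Protocol 8.9.1.2 also give PP its supportive role without one.

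**The concern.** A per-protocol set is meant to hold subjects who were managed as the protocol requires. Here a site that obeys the toxicity tables creates a major violator. The protocol's own examples of major violations (11.4.1) include a wrong treatment or incorrect dose; a directed stop is not among them.

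The rule also conditions on what happens after randomization. Of two subjects with one dose each, the one who dies by Day 7 stays in PP and the one who is alive and was stopped for toxicity leaves it. A death one day later, while dose 2 was still allowed, is removed. Death is the primary endpoint, so the set gains or loses primary events according to their date. Attributed toxicity may also differ between arms.

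The 5% condition is a separate matter. It contradicts three other passages, and it counts exclusions in total without regard to how they fall between arms, which is what a supportive analysis should reveal.

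**Working it through.** **1. Who is caught.** Only two doses are planned (Day 0 and Day 7), so a subject stopped after dose 1 cannot reach two.

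| Course after dose 1 | Protocol | Status under the SAP 7.3 two-dose rule |
|---|---|---|
| Grade 4 injection-site reaction | Permanent stop (Table 6-3) | Excluded |
| Other attributable Grade 3 or 4 toxicity | Permanent stop (Table 6-4) | Excluded |
| Grade 3 injection-site reaction or other attributable Grade 2, held, dose 2 never given | Hold (Tables 6-3, 6-4) | Excluded |
| Same, dose 2 given within the window | Hold, then dose | Two doses: not caught |
| Same, dose 2 given after the window | No rule stated | Two doses: not caught, but could be called a dosing deviation |
| Death by Day 7, one dose | – | Kept |
| Death on Day 8 before dose 2 | Dose 2 still in window | Excluded |

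The window is 7 − 1 = Day 6 to 7 + 1 = Day 8. The death exception ends at Day 7, which leaves a gap of one day.

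**2. The denominator for the 5% condition.** The planned size (Protocol 8.3, SAP 4) reproduces. Inputs are 45% and 30% mortality, 2:1 allocation, two-sided 0.05 and 80% power. With unpooled variance, the placebo n is (1.960 + 0.842)² × (0.45 × 0.55 + 0.30 × 0.70 / 2) / 0.15² = 7.85 × 0.3525 / 0.0225 = 122.98, so 123. Then 3 × 123 = 369, as stated. For 5% dropout, 123 / 0.95 = 129.5, so 130 placebo and 260 leronlimab, 390 in total.

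**3. The trigger.** SAP 9.2 does not name the denominator; the two populations are most naturally mITT and PP. Assuming all 390 are dosed:
- As a share of mITT: 0.05 × 390 = 19.5. PP runs at 20 or more exclusions and not at 0 to 19 (19/390 = 4.9%).
- As a share of PP: 19/371 = 5.1% and 18/372 = 4.8%. PP runs at 19 or more.

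**4. Range of effect.** The documents give no rate of toxicity-related missed second doses, so only bounds can be shown. Assume planning-level results of 78/260 = 30.0% on leronlimab and 58/130 = 44.6% on placebo (45% of 130 is 58.5, taken as 58), a difference of 14.6 points. Assume also that every exclusion is on leronlimab.

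| Excluded | All survivors | All deaths |
|---|---|---|
| 5 | 44.6 − 78/255 (30.6) = 14.0 | 44.6 − 73/255 (28.6) = 16.0 |
| 10 | 44.6 − 78/250 (31.2) = 13.4 | 44.6 − 68/250 (27.2) = 17.4 |
| 19 | 44.6 − 78/241 (32.4) = 12.3 | 44.6 − 59/241 (24.5) = 20.1 |

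Differences are in percentage points, from unrounded rates. The shift can go either way, and its sign depends on who is excluded.

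**The case against.** Requiring both doses is a legitimate, pre-specified exposure rule for PP. PP is supportive; mITT is the SAP's primary population and ITT a sensitivity analysis, and no multiplicity step depends on PP. The Day 8 gap is one day wide. If PP is distorted by selection, skipping it when few subjects are excluded does little harm. All of this stands as a limit on size. It does not justify calling a directed stop a violation, nor does it remove the conflict between SAP 9.2 and the other passages.

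A reader might infer four stronger points that the documents do not support.

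- *Every hold leads to exclusion.* The two-dose rule does not catch a subject who was held and later dosed.
- *A Grade 3 injection-site reaction leads to exclusion however it is handled.* This would need Section 5.3 to be a mandatory withdrawal rule. SAP 7.3 does exclude subjects who met withdrawal criteria and stayed in. But 5.3 speaks of investigator discretion and of reasons that may be recorded, so the toxicity item can be read as a recordable reason. The text is ambiguous.
- *The exclusions will be commoner on leronlimab.* In the completed trial in mild-to-moderate COVID-19 (Protocol 1.4.2.18), adverse events were reported by 34% on leronlimab and 50% on placebo, and serious events by 9% and 21%. Among 131 subjects given 700 mg in the HIV study (Protocol 1.5.2), the definitely related events were all mild or moderate injection-site reactions. Attribution is also blinded, so placebo subjects will be held and stopped too. Only a possible difference between arms can be claimed.
- *PP mortality on leronlimab could read 24.5%.* This needs 19 exclusions, all on leronlimab and all deaths. If all were for a missed second dose, each death must also fall after Day 7. At 19 of 390, with mITT as the denominator, SAP 9.2 would not run the analysis at all.

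**Conclusion.** The point holds in this form. SAP 7.3 excludes as major violators subjects who missed dose 2 because Tables 6-3/6-4 directed it, and subjects who died on Day 8 with dose 2 still allowed. PP membership thus depends on post-randomization events and on the date of the primary event. SAP 9.2 adds a condition that SAP 7.3 and Protocol 8.9.1.2 and 8.10.5 do not contain.

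The consequence is limited to a supportive analysis. The size of the distortion cannot be estimated from the documents, and the bounds above rest on assumed counts placed wholly in one arm. The figure of 0 to 19 unanalysed exclusions assumes that all 390 are dosed and that mITT is the denominator. The status of a Grade 3 injection-site reaction is an ambiguity to resolve, not a demonstrated contradiction.

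**What to change.** - **SAP 7.3.** Extend the death exception to the close of the V4 window (Day 8). Do not count non-receipt of dose 2 as a violation when the hold or stop was directed by Table 6-3 or 6-4, in either arm. Do not extend this to Section 5.3 in general: its list also covers voluntary withdrawal, loss to follow-up and inability to comply, and exempting those would largely empty the two-dose criterion.
- **SAP 9.2.** Delete the 5% condition, so that PP is run as SAP 7.3 and Protocol 8.10.5 state.
- **Protocol 5.3 and Table 6-3.** Reconcile these passages for Grade 3 injection-site reactions, so that the SAP criterion on withdrawal criteria met without withdrawal can be applied by program. Which handling is right is for the sponsor and its clinicians.

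The cost is a few lines of SAP text, one protocol clarification and one set of supportive tables. The adverse event record already holds grade, causality and effect on study treatment (Protocol 9.2), which the new rule can use. The change should be made before database lock, because PP membership is fixed before then.
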